### **Planned recruitment rate:**

In Phase 2, subjects are not recruited directly, but receive all diagnostic and treatment services from routine clinical staff. For the trial the evaluations and results are recorded. The estimated number of contacts is based on the number of active TB cases seen annually at these sites over the past 3-5 years; it seems unlikely there will be major changes in these numbers.

### **RANDOMIZATION:**

As described earlier in the Study Design section, the sites which receive the intervention of Phase 1 followed by Phase 2 will be selected randomly. Randomization will be stratified by country (See again Figure 3). As much as possible, within each country, the randomization of sites must result in reasonable balance in the number of contacts managed with and without the intervention. Because the number of patients with newly diagnosed pulmonary TB is not the same at all sites, a special procedure to ensure optimal balance will be undertaken. A total of 1000 randomization sequences will be generated (using a computer programme developed by [name] – biostatistician for this project). Each sequence will then be examined to verify the resultant balance in contacts who will and won't receive the interventions. Randomizations that result in reasonable balance will be selected. (In other studies this has meant approximately 200 of the 1000 randomization are selected). In the final step, one sequence is randomly selected from this sub-group of balanced randomization sequences.

### **SELECTING THE SOLUTIONS FOR PHASE 2:**

As part of the intervention, during Phase 2 health facilities will implement initial and in-service training, a standardized system for recording, reporting and monitoring, and additional site-specific solutions selected based on the analysis of Phase 1 results at that site. Potential site-specific solutions include conditional cash transfers, staff or patient incentives, and “one-stop shopping” (organization of services to deliver TST reading, medical evaluation, Chest X-ray, blood tests and initiation of LTBI therapy - all in one day and at the same clinic). The specific training/educational messages will be identified from Phase 1 results and incorporated into scripts prepared for teaching. If other organizational issues are identified as major barriers for index cases or contacts, then other potential service delivery improvements can be suggested.

The Phase 1 findings will be reviewed by the investigators from each country coordinating centre with the International Coordinating Centre (McGill) to identify the major problems and discuss potential solutions. Then the in-country investigators will meet TB program officials at the appropriate jurisdictional level (ie this may be at national or provincial/state, or at municipal level – depending on the organization of TB services within each country). At these meetings, the results of the Cascade analysis and the questionnaires/interviews from Phase 1 will be presented and used to pre-select a package of possible interventions to be 'pre-approved' by TB programme officials. Each of the possible options will be evaluated using an options analysis and simulation modelling exercise. With the collaboration of investigators at Liverpool School of Tropical Medicine we have developed a simple model, using discrete event simulation software, which uses site specific Phase 1 cascade data on LTBI cases seen, together with associated health system costs at each step in the LTBI cascade. This model also allows integration of cost and potential effect of proposed solutions to strengthen the cascade and thus provides real time cost effectiveness analysis for different solutions proposed. The effectiveness of solutions is based on systematic reviews of the published literature for each solution. The costs are based upon information from each site gathered by the site investigators during Phase 1. This tool was developed using Witness software with an arrangement from the company that the software will be provided to sites at no cost, as it is intended for use by site investigators and their Local TB Control Programs for future assessments, and decisions regarding further solutions to newly identified problems.

Next, the investigators from the country coordinating centres will meet administrators from the participating health facilities - to present the Phase 1 findings, and select the Phase 2 solutions. They will also explain the initial, and in-service training and recording/reporting methods, as well as review general aspect of the diagnosis and treatment of LTBI. The regimen to be used, selected as above by the responsible TB programme, will be reviewed. Note that within each country health facilities fall within one to four municipal or provincial jurisdictions. Therefore in Vietnam (2 provinces with 4 health centres each), and Canada (4 cities with one clinic each) results will be analyzed and presented and interventions selected, using the same options analysis approach described above, at the level of the city or province. On the other hand, all health facilities fall within one city in each of Ghana, Indonesia and Benin – hence Phase 1 results from all health facilities within each country will be used to select country-specific set of solutions. If there are substantial differences in Phase 1 findings between sites within each of these jurisdictions, then some solutions will be site-specific.

*[As examples: In Site A, the indicator data reveals that the step when most contacts are missed is the identification of contacts by newly diagnosed pulmonary TB patients. Responses from the questionnaires and interviews at this same site suggests that this occurs because health workers do not explain, and the patients do not understand the reasons for contact investigation. Therefore one cadre of health workers will be assigned this task (by health officials), and training around a scripted set of messages provided (by research staff) to that cadre of workers. In Site B, indicator data reveals that many contacts with positive TST fail to complete diagnostic evaluation. Questionnaire and interview information suggests this is because contacts must come at least 3 times to complete this – once for TST reading, a second time to see a physician, then a 3rd time to have a chest X-ray done. The intervention suggested will be to organize the service delivery so that all three activities can be completed on the same day – "one stop shopping".]*

**Financing of Solutions and LTBI expansion in Phase 2:**

Minimal funds will be provided by the study to sites to finance site specific solutions and cover any start up costs related to LTBI expansion (including initial and in-service training, including training materials, plus the development and implementation of new methods of recording, reporting and monitoring). Any ongoing, or recurrent costs must be borne by the public health system in each country. 100,000 CAN\$ will be budgeted for solutions and funds will be divided across sites based on the number of active cases at each site as well as the per capita GDP. Below are the amounts (CAD\$) that will be made available to each site:

Vancouver	\$17,449
Calgary	\$17,449
Benin	\$16,778
Ghana	\$16,778
Indonesia	\$20,134
Vietnam	\$11,409

The way in which the funds for solutions are spent is left up to each site (ie. all for one solution, or across several different ones). Additional funds are also provided to sites to purchase INH and Tuberculin.

**DESCRIPTION OF THE POTENTIAL SOLUTIONS:** *(Below are examples - to be selected and modified based on findings of Phase 1)*

**Training:**

Solutions to enhance the education of workers, PTB patients and their contacts seems almost inevitable. These educational materials will be selected from a host of materials already developed and available freely (for examples, see the CDC website: <https://findtbresources.cdc.gov/>), but their content will be modified

based on country specific findings from Phase 1. It is possible that in some sites more targeted solutions are necessary to overcome certain beliefs and attitudes (eg health workers who believe INH therapy of LTBI is useless, or will create drug resistance).

**Education of patients with active TB:** This will be done with a prepared script of key messages, identified from the questionnaires in Phase 1. Study staff will prepare the scripts and train clinic workers to deliver the teaching using these scripts.

**Education of health care workers** (physicians, nurses, and community health workers): Research staff will provide training to the different cadres of health workers at the participating sites – during the initial workshops and in-service site visits as described above. The key messages will be based on the findings in Phase 1. Lectures and other training materials that are prepared and delivered by research staff will also be given to TB program staff to assist in scale up activities later.

**Education of contacts starting LTBI therapy:** Scripts of key messages will be prepared, based on the questionnaires completed by contacts in Phase 1. Study staff will train clinic staff to educate contacts using these scripts.

### **Delivering the Initial Training:**

Prior to the start of Phase 2 – all health workers involved in the TB program from each site will receive training in the new system of recording and reporting of TB contact management. They will also receive training in contact management including Latent TB diagnosis and treatment. The LTBI regimen currently recommended by the National TB programme to be used through-out Phase 2 will also be reviewed.

About two weeks before Phase 2, a half-day training workshop will be held at each site (randomization unit). At this workshop the new methods of recording and reporting, plus basics of contact management will be reviewed, and problems encountered discussed. The major emphasis will be to present and discuss findings from Phase 1 at that site. These findings will be used to demonstrate the need for various solutions which will then be reviewed and discussed. A consensus will be reached about the solutions to be implemented, including any site-specific interventions, in that facility will be reached before closing the initial training workshops.

During the intervening weeks, research staff and investigators will make final preparations for any site specific solutions. A few days before the start of Phase 2, a final training meeting of 1-2 hours will be held at each site. During this session the site staff will receive any training needed for site-specific solutions (if any were selected for the site), plus a quick refresher about the procedures of contact investigation and treatment, as well as recording and reporting.

### **Delivering In-service training (site visits):**

Once the solutions are initiated at a site, research staff will come to the site weekly for 2 months, then every other week for 2 months, then monthly - for in-service training. During these visits the staff will review the new contact registries, and all other relevant records (such as the TB patient registries) to ascertain if new contacts have been identified and investigated. They will discuss with site staff any problems encountered, and reinforce the initial training - in terms of procedures for contact identification investigation and treatment, as well as recording and reporting. They will also train any new health workers assigned to contact management. In addition, once a month in the first 3 months, an investigator from the country coordinating centre will accompany the research staff - to discuss the contact management program with site staff, and reinforce messages and training.

### **Health services delivery:**

Solutions decided at this level will affect policy and budget. Hence the problems are likely to affect all sites within this jurisdiction, and any solutions will need to be approved by administrators for all sites. **Home visits to teach and screen contacts:** Site staff (not research staff) will visit homes of patients with active TB to identify their household contacts, and initiate symptom screening (for active TB) and screen, or refer for screening the eligible contacts. In many programmes in many LMIC community workers visit homes of patients with active TB to supervise treatment (ie they provide DOT). These workers could easily incorporate contact identification and education into their routine activities at little added cost. This intervention would be entirely under the control of, and hence at the discretion of, local health officials.

**Incentives for health workers:**

In jurisdictions where contact investigation is not mandated, it is likely that some incentives will be necessary in order to get programme staff to take on these added responsibilities. Compensation can be made for teaching sessions, (such as teaching patients with PTB or their contacts about the need for screening, teaching persons about to start LTBI therapy), or for each medication renewal visit. Incentives would have to be commensurate with usual salaries for the cadre of health workers involved. These incentives may be continued by TB programs after the study ends – several of the participating TB programmes already have similar incentives for detection and complete treatment of active TB. In other jurisdictions, (based on discussions with TB program managers there) we understand the TB programmes will add contact investigations to routine TB program activities, and adjust staffing accordingly.

**Coordinating service delivery** (“One stop shopping”): This would involve organizing services so that TST reading, medical evaluation, chest x-ray, any other necessary investigations and the decision to start LTBI therapy are all completed in the same place and on the same day. The research staff and investigators will invest the time for the administrative work required to create the service delivery models, including a check list of items to be arranged to ensure that the providers, support staff, and lab services are all present, and there is smooth flow of patients and information between services. However the sites will have to undertake responsibility for changes in staffing or other resources – again for sustainability reasons.

**Patient incentives and enablers:**

**Conditional cash transfers:** Another method to enhance completion of screening and diagnostic procedures is to offer to pay costs so that the contacts can visit the clinics, for administration and reading of TST, symptom screening, and further evaluation if needed, or to reimburse costs for Chest X-rays. This implies that this type of transfer payment programme is available within the country, and at that site – which is the case in some, but not all countries..

**PHASE 2 ENHANCED REPORTING:**

**Contact Management Registries**

A new registry book will be developed to record the key diagnostic and treatment steps in contact management. To facilitate their later adoption by health facilities as part of routine TB control activities, these contact registries will be modeled after the Active TB Treatment Registries of national TB programs that are currently used in all DOTS programmes and recommended by WHO .

The Contact Registry will include identifying information for each new patient with active pulmonary TB, as well as identifying, and demographic information for all identified contacts. The results of screening tests, plus Chest X-ray and medical evaluation for the TST (or IGRA) positive contacts will be included, as well as initiation and completion of LTBI treatment. Information on LTBI treatment starts from these registries will be compared to the other methods of ascertainment of the primary outcome – in the final 6 months – in secondary analysis

**Reporting:**

The Contact Management registries will be used to generate quarterly reports of diagnoses of contacts, and cohort reports of treatment outcomes in TST positive contacts. These quarterly reports will be modeled after the quarterly reports of case finding, and treatment outcomes that are recommended by WHO , and used by the National TB control programmes in almost all LMIC.

The quarterly reports will be based on data abstracted from the Registries (they are designed to be abstracted very easily), and initially prepared by study staff. These reports will include the number of new pulmonary TB patients, household contacts identified, investigated with symptom screening and TST, had TST reading, TST positive who underwent medical evaluation, and initiated LTBI medication.

**LTBI related activities at Control sites:**

At the control sites, investigators will work with local TB programmes to ensure that staff have access to materials (PPD and INH), as well as possess the skills necessary for basic management of latent TB. These skills will include tuberculin skin test techniques as well as understanding of the current local standard for treatment of latent TB (usually 6-months INH as recommended by WHO.) Note that investigators will facilitate this work, but the primary responsibility will remain with the local TB control programs to ensure that the control sites have LTBI management policies and procedures in place.

**DATA ANALYSIS FOR PHASE 2****Contact investigation outcomes:**

Among the household contacts, the following outcomes will be measured

1. Contacts identified.
2. **Started LTBI therapy** (primary outcome)
3. Completed LTBI therapy (secondary outcome)

The primary outcome will be the proportion of identified contacts who start LTBI therapy – in the final 6 months of the trial (to account for delayed impact of this complex intervention). If we find that more than 20% of contacts are diagnosed to have active TB, which would be far in excess of published experience, then we would investigate if this reflected over-diagnosis.

Our analysis will be performed at the level of the individual, but will account for correlation between subjects from the same centre. Population averaged logistic regression with an identity link estimated via generalized estimating equations (GEE) and using a jack-knife estimate of the variance will be used to assess the effect of the intervention on the primary and secondary outcomes above, depending on the type of outcome (e.g. count or proportion). This approach will account for the correlation between subjects in the same cluster, and for varying cluster sizes. Using an identity link (rather than a logit link) will allow us to estimate risk differences for binary outcomes.

Population averaged models estimated via GEE are robust to mis-specification of the correlation structure. While our data will surely have clustering at the household level as well, we need only account for the top-level cluster (here centre) and use the empirical standard errors to ensure that our inferences are conservative.

For count type outcomes, we will use a similar approach as described above, but using a Poisson distribution.

In secondary analyses, we will use logistic regression with a logit link estimated via GEE and also adjust for additional confounders (country, age, sex and smear status of index case). In sensitivity analyses we will analyze at the level of the cluster. Missing data will be dealt with via multiple imputation using chained equations which will allow us to impute binary as well as continuous variables .

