### **Study Objectives:**

**Primary:** To evaluate the effectiveness of a standardized public health evaluation followed by targeted solutions for problems identified to increase the proportion starting LTBI treatment among household contacts of patients with active pulmonary TB, during the last 6 months, of an 18 month cluster randomized trial;

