**Calgary:** In Calgary, all patients newly diagnosed with active PTB are assigned a public health nurse who is based at the Calgary Public Health TB Clinic. This nurse interviews the family in the clinic, or if this cannot be arranged, the nurse will make a home visit. Identified contacts that do not come to clinic are contacted via telephone twice and if unsuccessful, a letter is sent on two occasions. Contacts that live in the city of Calgary are referred to the Foothills hospital TB clinic for evaluation. If they do not come the public health nurse will call them twice. If LTBI is diagnosed, LTBI therapy is individualized. Individuals who drop out during LTBI therapy are called by clinic staff.

**Benin:** The Benin NTP policy is to ask all newly diagnosed active pulmonary TB cases to bring all children aged under 5 living in the same household to the nearest TB treatment facility for evaluation. The patient is also asked to advise all symptomatic household contacts to visit diagnostic centres for evaluation. Home visits are not done to identify or screen contacts. The adult and pediatric 4RIF vs 9INH trials are being conducted at the Centre National de Pneumo-Phthisiologie (CNPP) in Cotonou. The randomization units for the proposed trial will be two independently staffed treatment centres in Cotonou – the CNPP, and the Centre de Akron a Portonovo.

**Ghana:** In Kumasi, Ghana, all patients newly diagnosed with active pulmonary TB are interviewed, and screened for symptoms of active PTB. Contacts that do not have symptoms are not assessed further except for children under the age of 5 and known HIV infected persons – who are referred to the hospital TB clinic, where they receive 6 months INH. Individuals who drop out during LTBI therapy are contacted by telephone.

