### **Ascertainment of study outcomes - at all sites:**

Ultimately, in the intervention sites we will be able to use the newly developed and introduced Contact Management Registries (see below) to extract all necessary information and outcomes – including number of pulmonary TB cases (Index cases), number of contacts identified, and number who initiate LTBI therapy. However, these detailed contact registries are considered an integral part of the public health intervention, since considerable training in recording and reporting as well as the procedures of contact management will be needed for these to be completed accurately and completely. Introduction of these registries at control sites would be difficult without extensive training; if such training was given at the control sites, this would constitute a partial intervention, and reduce potential differences between intervention and control sites.

Hence recording of outcomes at control and intervention sites must rely on simple measures that can be implemented with minimal training, prior to the start of the trial at all sites. It is important that the procedures to ascertain (measure) these outcomes be established at the beginning of Phase 1, and continue **unchanged** at all health facilities (both intervention and control facilities) through-out the 18 months of the study.

Identification of contacts may not be performed, or not clearly recorded at all health facilities – especially the control facilities. This is why we must carefully document the number of index patients with active pulmonary TB diagnosed at each site. When the study is completed, the coordinating centre may use the number of index cases to estimate the number of household contacts that likely could have been identified (see Analysis section) Data sources will vary by site, depending what methods of documentation are already being used. We will collect information on the number of newly diagnosed index cases from lab or other sources that report active cases. The number of household contacts indentified will come from different sources depending on what is available the site. Finally, we will estimate the number of contacts who start LTBI treatment from hospital and or clinic records using a standard data collection form in all sites. The number of contacts completing LTBI therapy will be estimated retrospectively from clinic records.

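### The primary outcome is divided by identified contacts, a post-randomisation count that the intervention is meant to raise, so the effect can be diluted or reversed if identification differs between arms

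*Protocol*

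**What the plan says.** The primary objective (Study Objectives) is "to increase the proportion starting LTBI treatment among household contacts of patients with active pulmonary TB". It is not restricted to contacts whom a clinic has listed, and neither is the study hypothesis.

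The Phase 2 analysis section narrows this: "The primary outcome will be the proportion of identified contacts who start LTBI therapy", measured in the final 6 months and analysed at individual level by GEE with clustering by centre. The same section lists "Contacts identified" as an outcome in its own right.

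Other sections show that the package works on identification. In the Site A example under Selecting the Solutions for Phase 2, the problem to be solved is that "the step when most contacts are missed is the identification of contacts by newly diagnosed pulmonary TB patients". Health Services Delivery offers home visits for finding household contacts. At the in-service visits, research staff check whether new contacts have been identified and investigated.

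The section on ascertainment of outcomes at all sites concedes: "Identification of contacts may not be performed, or not clearly recorded at all health facilities", and adds that this applies particularly to control facilities. For the period after the trial has ended, it offers a remedy: "the coordinating centre may use the number of index cases to estimate the number of household contacts that likely could have been identified". For this it points to the Analysis section. The Phase 2 analysis section has no such step. A formula for expected contacts appears in the Data analysis section of the Phase 1 chapter, where the expected number is compared with the number identified.

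**The concern.** Randomisation makes the clinics comparable, and with them the households of their index patients. It does not make comparable the subsets of contacts whom the clinics choose to list. A denominator that the intervention enlarges can hide a real gain. A clinic that finds many more contacts and treats more of them can show the same proportion as before, or a lower one.

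The composition of the lists may differ too. Usual care in Benin is to "ask all newly diagnosed active pulmonary TB cases to bring all children aged under 5 living in the same household" and to advise symptomatic contacts to attend. In Ghana, contacts without symptoms are assessed further only if they are under 5 or known to be HIV-infected. In Indonesia, with 8 of the 24 randomisation units in Table 1, contact screening is described as rarely done and not recorded. Control lists there may be short and selected. A clinic that lists nobody contributes no records to an individual-level GEE, so a randomised cluster with the poorest contact work would leave the primary comparison.

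At stake is whether the primary result answers the stated objective, and whether the stated power applies to it.

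**Working it through.** **1. The protocol's own figure.** Inputs from Sample size considerations and Table 2: control proportion 0.10, detectable difference 0.10, ICC 0.05, 100 contacts per clinic, 24 clusters (12 per arm if allocated 1:1), alpha 0.05 (taken as two-sided), power 80%.

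- Design effect = 1 + (100 - 1) × 0.05 = 5.95 (stated 6.0).
- Unclustered size for 10% vs 20%, no continuity correction: [1.96 × √(2 × 0.15 × 0.85) + 0.8416 × √(0.10 × 0.90 + 0.20 × 0.80)]² / 0.10² ≈ 199 per arm.
- 199 × 5.95 ≈ 1184 per arm, against 1214 stated (within 3%). Power at 12 × 100 = 1200 per arm is 80.5%.

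The figure reproduces. Read as power for the stated objective, it takes identification to be the same in both arms.

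**2. Condition for dilution and reversal.** Let *s* be starts per household contact and *i* the fraction of household contacts identified. The planned outcome is *p* = *s* / *i*. The intervention arm shows the higher *p* only if

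s(int) / s(con) > i(int) / i(con).

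If starts and identification rise by the same factor, the observed difference is zero. If starts rise by the smaller factor, the sign reverses. This holds whatever the actual fractions are.

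**3. Size under assumed fractions.** Assume the intervention doubles *s* and 10% of identified control contacts start. Then p(int) = 2 × 0.10 × i(con) / i(int), while the true difference per household contact is 0.10 × i(con). Power uses ICC 0.05 with the analysed number held at 1200 per arm.

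| Identified, control / intervention | Ratio of identification | True difference per household contact | Observed p, control vs intervention | Observed difference | Power |
|---|---|---|---|---|---|
| 70% / 70% | 1.00 | +7.0 points | 10% vs 20.0% | +10.0 points | 80% |
| 70% / 80% | 1.14 | +7.0 | 10% vs 17.5% | +7.5 | 59% |
| 70% / 90% | 1.29 | +7.0 | 10% vs 15.6% | +5.6 | 39% |
| 50% / 70% | 1.40 | +5.0 | 10% vs 14.3% | +4.3 | 26% |
| 50% / 90% | 1.80 | +5.0 | 10% vs 11.1% | +1.1 | about 5% |
| 50% / 100% | 2.00 | +5.0 | 10% vs 10.0% | 0 | – |
| 30% / 90% | 3.00 | +3.0 | 10% vs 6.7% | -3.3 | – |

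Every row has the same true doubling of starts per household contact; only identification changes.

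**4. Does the protocol already close the gap?** The ascertainment section allows an estimate from index cases but does not require it, and defers it until the data are complete. The section that defines the primary analysis keeps identified contacts. The Phase 1 formula (index cases × average contacts per case) is used to describe a shortfall, not as a denominator. Covariate adjustment (country, age, sex, smear status of the index case) appears only in secondary analyses. Neither that adjustment nor multiple imputation restores contacts who were never listed.

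**The case against.** The strongest reply is that the authors saw the problem. They say that index cases are counted because identification may fail. The Study Outcomes section groups index cases, identified contacts and starts as primary study outcomes, counted monthly everywhere. The Analysis section they point to could be the Phase 1 Data analysis section, and a SAP that is not shown could say when the estimated denominator applies. Ascertainment procedures are also to stay unchanged at all facilities. What stands is that the raw material for a sound outcome exists. What does not is that the outcome is thereby fixed: the protocol names identified contacts as the denominator, and the alternative is discretionary, in a trial where clinic staff are unblinded. Unchanged procedures do not stop real identification from rising in one arm.

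Three stronger readings are tempting, and the documents do not support them.

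- *The comparison is biased, and will reverse.* A reader might infer this, but distortion needs identification to differ between arms, and no fraction by arm is given. With equal and comparable identification there is none. Its direction also depends on who is identified.
- *Control clinics in general list only those they treat.* Benin has 2 of the 24 units. In Vietnam (8 units) usual care already lists eligible household contacts but treats few, and nurses in Canada interview patients or families. Indonesia does support the worry. A scenario in which control clinics list a handful of mostly treated children is an extreme case.
- *The outcome is undefined where a clinic lists nobody.* In the individual-level primary analysis the clinic drops out and the arm-level proportion stays defined. Only the cluster-level sensitivity analysis would have an undefined value.

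**Conclusion.** The concern holds in this form: the primary denominator is a post-randomisation count that the intervention is designed to raise, it differs from the population in the objective, and the protocol's remedy is neither binding nor carried into the Phase 2 analysis. Dilution or reversal is a possibility that the protocol's own text makes plausible. It is not a certainty.

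The algebraic condition for reversal needs no assumed fractions. The sizes do: they rest on assumed identification fractions, a true doubling of starts per household contact, the protocol's 10% control rate and ICC of 0.05, and a fixed analysed number. On those terms, a modest gap in identification (70% vs 90%) roughly halves the power, and a wide one (30% vs 90%) gives the wrong sign. This should be settled before the outcome data are examined, because choosing the denominator afterwards would add a second problem.

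**What to change.** Prespecify one primary outcome with a denominator built from index cases: household contacts starting LTBI treatment per index case with microbiologically confirmed pulmonary TB, in the final 6 months. Analyse it as a clinic-level count with log(index cases) as offset, using Poisson GEE with clustering by clinic and accounting for the stratification by country. The protocol already provides a Poisson GEE for counts. A clinic that lists nobody then contributes a count of zero instead of disappearing.

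Starts per expected household contact, with one fixed multiplier per country applied to both arms, is a possible alternative. It is not equivalent when multipliers differ between countries, so choose one of the two in advance.

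Keep identified contacts per index case and starts per identified contact as secondary cascade measures. Replace the optional wording in the ascertainment section with the chosen rule, and align the Phase 2 analysis section with it.

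Cost: changes of wording and no new data, since index cases and starts are already counted monthly at all facilities. The power statement must be redone on the new scale. Index-case counts could themselves rise a little through cases found among contacts. With the 2–5% yield cited in the Background and 4.2 contacts per case, the upper bound is 4.2 × 0.02 = 0.08 to 4.2 × 0.05 = 0.21 extra cases per index case, if every contact is investigated and every such case is new and confirmed. Exclude these co-prevalent cases from the denominator, or check their influence in a sensitivity analysis.
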